7.7.2 Laboratory Evaluations

Data for the following hematology, blood chemistry, lipid profile, and urinalysis received from central laboratory will be listed and summarized by treatment group and visit. If data for any additional analytes are also received then these will be listed only.

All summaries of laboratory test results will be presented in International System of Units (SI) and conventional units. Out-of-reference-range values will be flagged as high (H) or low (L) in the listings.

For analysis purposes, values preceded by a "<" or a ">" sign (ie, those below or above the limits of quantification) will be considered equal to the lower or upper limit of quantification, respectively.

Laboratory evaluations measured on a continuous scale will be summarized by visit using standard descriptive statistics for the Safety population. Changes from Baseline will also be summarized. For analysis by visit, the nominal study visits will be utilized.

Statistical Analysis Plan

Teijin America, Inc.
TMX-049DN-201

Qualitative urinalysis laboratory results will be summarized for Baseline and all scheduled post-baseline study weeks as the number and percentage of patients having either positive or negative results. Missing category will be reported if there is more than 1 patient reported in any treatment group.

For each laboratory analyte, the Baseline value will be defined as last scheduled or unscheduled value collected prior to the first dose of treatment.

For hematology and serum chemistry, shift tables presenting movement in and out of reference range from Baseline to each scheduled post-Baseline visit will be provided for each treatment group.

Mean change from Baseline with standard deviation bars will be plotted by visit for select laboratory parameters for the Safety Analysis Set.

The lab parameters collected are presented in the following table:

Statistical Analysis Plan

Teijin America, Inc.
TMX-049DN-201


Serum Chemistry: Aspartate aminotransferase (AST) Alanine aminotransferase (ALT) Alkaline phosphatase Gamma glutamyl transferase (GGT) Lactate dehydrogenase (LDH) Sodium Potassium Chloride Calcium Bicarbonate Inorganic phosphate Glucose Urea Uric acid (sUA) Total bilirubin Direct bilirubin Creatinine Blood urea nitrogen (BUN) Total protein Albumin Creatinine phosphokinase (CPK) Glycosylated hemoglobin (HbA1c)
	
Complete Blood Count White blood cell count (WBC) Red blood cell count (RBC) Hemoglobin Hematocrit (PCV) Mean cell volume (MCV) Mean cell hemoglobin (MCH) MCH concentration (MCHC) Platelet count Differential WBC

	
Urinalysis: Microscopic examination Specific gravity pH Protein Glucose Ketones Blood Urobilinogen

	
For Females Only: Urine pregnancy test

	
For Postmenopausal Females Only: Follicle-stimulating hormone (FSH)

Lipid Panel: Total cholesterol High-density lipoprotein cholesterol (HDL-C) non-HDL-C
	
Serology: Hepatitis B surface antigen (HBsAg) Hepatitis C antibody Human immunodeficiency virus (HIV)

	
Urinary Biomarkers: Urinary albumin-to-creatinine ratio (UACR) Kidney injury molecule 1 (KIM-1) Liver fatty acid binding protein (L-FABP) 8 hydroxy 2' deoxyguanosine (8-OHdG) N-acetyl-β-D-glucosaminidase (NAG)

Thyroid Testing: Triiodothyronine (T3) Thyroxine (T4) Free triiodothyronine (FT3) Free thyroxine (FT4) Thyrotropin/Thyroid stimulating hormone (TSH)
	
Blood Biomarkers: Soluble tumor necrosis factor receptor 1 (sTNFR1) high sensitivity C reactive protein (hs-CRP) Estimated glomerular filtration rate (eGFR)

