7.10.4.4 Statistical Analysis of Safety

Safety evaluation will include incidence of AEs (or TEAEs), laboratory test results, vital signs, ECG results, and physical examination findings. All summaries of safety data will be based on the Safety Population. No formal statistical analysis of the safety data will be performed. There will be safety summary tables produced and no modeling of data.

Summary tables will be provided for all AEs by treatment group. The incidence of AEs, AEs related to study medication, SAEs, and AEs leading to discontinuation of the study treatment will be presented by MedDRA (Medical Dictionary for Regulatory Activities) system organ class (SOC) and preferred term. In addition, the incidence of AEs by severity will be presented by SOC and preferred term.

The AE summary tables will include counts of subjects. Therefore, if a subject experiences more than 1 episode of a particular AE, the subject will be counted only once for that event. If a subject has more than 1 AE that is coded to the same preferred term, the subject will be counted only once for that preferred term. Similarly, if a subject has more than 1 AE within a SOC, the subject will be counted only once in that SOC.

Laboratory test variables will be summarized by treatment group and visit using descriptive statistics (number of subjects, mean, SD, minimum, median, maximum, as well as mean change from Baseline, and number and percent of subjects within specified categories). Shift tables (ie cross-tabulations of below the lower limit of the normal range, within the limits of the normal range and above the upper limit of the normal range at Baseline versus scheduled visits) will be presented by laboratory test. Laboratory tests with categorical results that cannot be analyzed by change from Baseline or shift table analysis will not be included in these summaries, but will be listed. Data obtained from laboratory tests not required by the

protocol will not be summarized, but will be listed.

Descriptive statistics of vital signs and ECG results at each visit will be presented by treatment group. Physical examination findings will be listed for each subject.

No inferential safety statistical analysis will be performed.

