8. RISKS AND BENEFITS

TMX-049 is proposed for development as a therapeutic drug for the treatment of hyperuricemia associated with gout and DKD.

In non-clinical studies, TMX-049 was suggested to have more stable uric acid-lowering effect than existing drug, and TEI-R04969 showed a persistent XO inhibitory effect in blood vessels compared to existing drug, suggesting the possibility that TMX-049 can improve vascular endothelial function also in the clinical setting. Also, TMX-049 is considered to be a new drug candidate for the treatment of DKD.

Two important potential risks, gouty arthritis and interaction with azathioprine or mercaptopurine have been identified. No important identified risks have been identified. In this study, these important potential risks can be minimized by exclusion of gouty arthritis patients and prohibition of the concomitant use of the drug with azathioprine or mercaptopurine. There will be no restrictions on medication for gouty arthritis, so that the possible burden on subjects would not be beyond acceptable even in cases where gouty arthritis were observed.

There were 4 other safety concerns from non-clinical studies, calculi in the urinary organs, effects on the thyroid, increased ALT levels, [REDACTED]

[REDACTED] Since no related findings were noted in the clinical studies, these non-clinical toxicity findings (calculi in the urinary organs, effects on the thyroid, and increased ALT levels) are not identified as important risks. The interactions with transporter or metabolic enzyme-related drugs are not identified as important risks since there are no clinical data, and effects on drug exposure in humans are unknown. In this study, some of these transporter or metabolic enzyme-related drugs which possibly raise safety concerns will be prohibited.

Based on current knowledge, the benefit-risk balance of TMX-049 remains positive.

More detailed information about the known and expected benefits and risks and reasonably anticipated AEs of TMX-049 may be found in the IB.¹¹

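### SAP 7.7.2 plans fewer laboratory outputs than Protocol 7.10.4.4 and does not declare it: no thyroid or lipid shift tables, no specified-category counts for continuous tests, and no count of ALT/AST elevations by degree

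*SAP*

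**What the plan says.** **Protocol 7.10.4.4 (Statistical Analysis of Safety).** Laboratory variables are summarised by treatment group and visit with descriptive statistics, "as well as mean change from Baseline, and number and percent of subjects within specified categories". Shift tables by normal range, "at Baseline versus scheduled visits) will be presented by laboratory test", are not restricted to particular panels. The only exception is categorical results that cannot be analysed in this way. The synopsis names five safety laboratory panels, and thyroid testing is one of them. Appendix A has thyroid tests and lipids taken at Visits 2 to 7.

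**SAP 7.7.2 (Laboratory Evaluations).** The opening sentence names hematology, blood chemistry, lipid profile and urinalysis for listing and summary, then adds: "If data for any additional analytes are also received then these will be listed only". Continuous evaluations are summarised by visit, with changes from Baseline. Shift tables are planned as follows: "For hematology and serum chemistry, shift tables presenting movement in and out of reference range from Baseline to each scheduled post-Baseline visit". Timing is by nominal visit: "For analysis by visit, the nominal study visits will be utilized". The section ends with a table of the parameters collected, which includes T3, T4, FT3, FT4 and TSH.

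**SAP section 8 (Changes in Planned Analysis)** reads as not applicable. SAP section 1 gives the protocol of 07 FEB 2018 as its source, which is the protocol reviewed here.

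**Protocol section 8 (Risks and Benefits)** states: "There were 4 other safety concerns from non-clinical studies, calculi in the urinary organs, effects on the thyroid, increased ALT levels". It adds that these findings are not classed as important risks, because no related findings had been noted clinically.

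**The concern.** Safety and tolerability is a stated objective. The multiple-dose Phase 1 studies described in Protocol 5.4.2 and 5.4.3 dosed for 10 days, whereas this trial doses for 12 weeks at up to 200 mg. Thyroid and ALT were singled out from toxicology: follicular cell hypertrophy in the 4-week rat study, and raised ALT at the top dose in the 16-week monkey study. Protocol 5.4.2 also reports one mild transaminase increase at 120 mg that was judged an adverse drug reaction.

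For these two concerns the most useful displays are movement across the reference range (thyroid) and the number of subjects with marked elevations in each arm (ALT/AST). As written, the SAP gives no shift table for thyroid and no count by degree for ALT/AST. A difference between arms in the number of marked elevations would have to be assembled from listings. A narrowing that SAP section 8 does not record is also easy to miss when the study report is written.

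**Working it through.** No figure in the plan needs reproducing. The main check is to compare the two documents output by output.

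| Output | Protocol 7.10.4.4 | SAP 7.7.2 (with 7.1) |
|---|---|---|
| Descriptive statistics and change from Baseline | Laboratory variables, by arm and visit | Kept for continuous tests: N, mean, SD, median, minimum, maximum. Thyroid status unclear |
| Low/normal/high shift tables | By laboratory test | Hematology and serum chemistry only |
| n (%) within specified categories | Required; categories not defined | Not carried over. n (%) appears only for positive/negative urinalysis, plus the range cells of the shift tables |
| Declared change | – | Section 8: none |

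**Thyroid and lipid shift tables.** There are five thyroid tests (T3, T4, FT3, FT4, TSH) and four post-baseline visits (Visits 4, 5, 6 and 7), and 5 × 4 = 20 baseline-to-visit comparisons per arm without a shift table. The three lipid tests (total cholesterol, HDL-C, non-HDL-C) add 3 × 4 = 12.

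**Thyroid summaries.** Two readings are possible. The opening sentence omits thyroid and sends additional analytes to listings. The parameter table includes thyroid, and the sentence on continuous evaluations is not limited by panel. The text does not settle which reading applies.

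**ALT/AST.** Both are in the Serum Chemistry panel, so both get by-visit statistics and shift tables. What a by-visit maximum and an above-range count leave out can be shown with an illustration. The planned arm size is 132/3 = 44. The ULN (40 U/L) and the value in the other subjects (25 U/L) are assumptions, because the documents give neither.

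- One subject at 8 × ULN raises the arm mean by (8 × 40 − 25)/44 = 295/44 = 6.7 U/L. With ULN 35 and others at 30 the rise is (280 − 30)/44 = 5.7. With ULN 50 and others at 20 it is (400 − 20)/44 = 8.6.
- Arm A has one subject at 320 and two at 41. Arm B has one at 320 and two at 200. The other 41 subjects in each arm are at 25.
- In both arms the maximum is 320 and the above-range count is 3.
- The means are (320 + 82 + 1025)/44 = 32.4 and (320 + 400 + 1025)/44 = 39.7.
- Subjects above 3 × ULN (120 U/L) number 1/44 (2.3%) in Arm A and 3/44 (6.8%) in Arm B.

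The means differ, but no planned laboratory table gives the 1 versus 3. Nor does any laboratory table cross ALT/AST with bilirubin, although Protocol 7.3.3.2 uses that combination.

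**Unscheduled values.** Protocol 7.6.2.6 allows extra laboratory tests when clinically appropriate. The on-treatment visits are at Days 14, 42 and 84, so the later gaps are 28 and 42 days. A criterion in 7.3.3.2 that depends on persistence beyond 2 weeks will often need an off-schedule recheck. SAP 7.7.2 admits unscheduled values when it defines Baseline, but says only that by-visit analysis uses nominal visits. A peak found at a recheck may therefore enter no by-visit table.

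**The case against.** Several stronger readings are tempting, and the documents do not support them.

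- *That ALT is shown only as in or out of range.* It is not. By-visit descriptive statistics and changes from Baseline are planned, and SAP 7.1 includes the maximum. A very high value at a scheduled visit would appear there.
- *That the two concerns cannot be seen in any table.* This is also too strong. Events reported by investigators enter the treatment-emergent adverse event tables of SAP 7.7.1, including those for severity and discontinuation. SAP 7.2 tabulates reasons for early discontinuation. These routes depend on how a laboratory finding is reported, but they exist.
- *That thyroid is definitely listed only.* The parameter table makes inclusion in the summaries a fair reading. Only the loss of shift tables is certain.
- *That thyroid's absence from the SAP 6.1 window headings matters.* SAP 7.7.2 uses nominal visits for laboratory summaries, so it changes nothing here.
- *That the protocol requires counts by multiples of the ULN, joint ALT/bilirubin counts or worst-value tables.* It does not. Its categories are undefined, and its shift tables are low/normal/high against scheduled visits, which the SAP delivers for ALT.
- *That the protocol excludes repeat ALT results from summaries.* The sentence beginning "Data obtained from laboratory tests not required by the" protocol concerns tests that the protocol does not call for. ALT is a required test, so applying the sentence to unscheduled repeats is an inference.

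Two further points count against the concern. SAP 7.1 refers to table shells that are not in the documents and that might hold categories. Protocol 5.4.1 and 5.4.3 report no clinically significant endocrine findings in Phase 1. The first does not close the gap in the SAP text. The second lowers the urgency but does not remove the protocol's requirement.

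**Conclusion.** The point holds as a narrowing of scope that the SAP does not declare. Three parts rest directly on the text:

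- Thyroid and lipid tests have no shift tables (20 and 12 baseline-to-visit comparisons per arm).
- The protocol's n (%) within specified categories is not carried over for continuous tests.
- SAP section 8 records no change.

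The summary status of thyroid tests is ambiguous rather than excluded. For ALT/AST the gap is limited: level and range status are shown, but the number of subjects by degree of elevation, or with combined bilirubin elevation, is not. Values from unscheduled rechecks may be missed by the by-visit tables. The numerical ALT illustration depends on the assumed ULN and background values. The finding does not.

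**What to change.** In SAP 7.7.2:

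1. Name thyroid testing among the summarised panels, and extend the shift tables to thyroid and lipid tests. This restores what Protocol 7.10.4.4 requires.
2. Define the protocol's specified categories. By arm, add n (%) of subjects whose worst post-baseline value, scheduled or unscheduled, exceeds the multiples already stated in Protocol 7.3.3.2: ALT or AST above 3, 5 and 8 × ULN, and above 3 × ULN with total bilirubin above 2 × ULN. These levels would be used for reporting only and imply no change to subject management. INR is left out of the joint count because Appendix A lists no INR test.

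Item 2 is an improvement rather than an express protocol requirement. If the sponsor prefers the narrower outputs, SAP section 8 should record each departure and its reason. No change to the SAP 6.1 windows is needed.

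The cost is a few lines of SAP text and a few extra tables from data already collected, with no change in trial conduct.

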7.3.3 Withdrawal of Subjects

7.3.3.1 *Replacement Procedures*

Subjects who are withdrawn or who choose to withdraw from this study will not be replaced.

7.3.3.2 *Guidance to Investigators on When to End Study Treatment Regimen*

Subjects will be withdrawn if any of the following criteria are met:

- subject decision (withdrawal of consent)
- any clinically relevant signs or symptoms that in the opinion of the Investigator warrant subject withdrawal
- ALT or AST >8 x ULN
- ALT or AST >5 x ULN for more than 2 weeks
- ALT or AST >3 x ULN and with either a total bilirubin >2 x ULN or and International Normalized Ratio (INR) >1.5
- ALT or AST >3 x ULN with the appearance of fatigue, nausea, vomiting, right upper quadrant pain or tenderness, fever, rash, and/or eosinophilia (>5%)
- eGFR ≤ 15 ml/min/1.73m², confirmed with repeat measurement
- development of an inter-current illness, condition, or procedural complication that in the opinion of the Investigator would interfere with the subject's continued participation
- development of an intolerable AE as determined by the Investigator and/or subject
- positive pregnancy test result
- significant protocol non-compliance in the study, as considered applicable by the Investigator
- if it becomes necessary to break the blinding code for a subject

A subject is free to withdraw from the study at any time for any reason without prejudice to their medical care. In addition, the Investigator may decide, for reasons of medical prudence, to withdraw a subject. In either event, the Sponsor will be notified and the date and reason(s) for the withdrawal will be documented in the subject's source data. Should the randomization code be broken for a subject, the date, time, and reason will be recorded in the subject's source data.

The Investigator will also withdraw the subject from the study upon the request of the Sponsor or if the Sponsor terminates the study. Upon occurrence of a serious or intolerable AE, the Investigator should confer with the Sponsor before discontinuing the subject.

If a subject has started the investigational medicinal product (IMP) and subsequently develops an inter-current medical problem, the Investigator may decide to withdraw IMP administration temporarily on clinical grounds. If the subject recovers and there are no clinical contraindications to resuming IMP administration this should be allowable within the protocol if the treating clinician feels it is appropriate to do so.

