7.6.2.6 Clinical Laboratory Evaluations

Blood and urine samples will be collected for clinical laboratory evaluations at the times indicated in the Schedule of Assessments ([Table 2](#)).

Additional clinical laboratory evaluations will be performed at other times if judged to be clinically appropriate or if the ongoing review of the data suggests a more detailed assessment of clinical laboratory safety evaluations is required.

An Investigator will perform a clinical assessment of all clinical laboratory data.

The evaluations to be performed are listed in [Appendix A](#).

The results of UACR and sUA at Visits 3, 4, 5, 6, and 7 will not be reported Investigators, subjects, and the Sponsor staff. Investigators must not measure UACR or sUA at local sites.

7.6.2.7 *Blood Sample for HbA1c*

A blood sample will be collected for the measurement of HbA1c at the times indicated in the Schedule of Assessments (Table 2).

7.6.2.8 *Physical Examinations*

Full physical examinations will be performed at the times indicated in the Schedule of Assessments (Table 2).

7.6.2.9 *Body Weight*

Body weight (in underclothes) will be recorded at the times indicated in the Schedule of Assessments (Table 2). Body weight should be taken at the same time of day, and using the same equipment.

7.7 **Pharmacokinetic Analysis**

7.7.1 **Blood Sampling for the Analysis of Plasma TMX-049**

Blood samples (approximately 1 x 5 mL) will be taken by venipuncture or cannulation at the times indicated in the Schedule of Assessments (Table 2).

Samples taken from subjects in placebo group will not be analyzed.

At Visit 4, a sample will be obtained prior to TMX-049 dosing (trough sample).

At Visit 5, a sample will be obtained 3 ± 1 hours after study medication dosing (t_{max} sample). The timing of dosing can be adjusted to the time of visiting.

At Visit 6, a sample will be obtained ≥ 6 hours (the ideal target is ≥ 8 hours) after study medication dosing (elimination phase sample).

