6.1 Time points and Visit Windows

Day 0 is defined as the Baseline/Randomization visit (Study Visit 3). Day 1 is the first day of treatment. Relative days after Day 1 are calculated as (assessment date – Day 1 date) + 1. Relative days prior to Day 1 are calculated as (assessment date – Day 1 date).

The visit windows defined in the following table will be used for the by-visit analyses of the primary, the secondary and other endpoints. All other analyses will use the nominal study visit as defined in the study schedule and eCRF.

If there are multiple visits (scheduled or unscheduled) within a visit window, the measurement closest to the target day of the visit will be used in the analysis. If the measurements are equally distant to the target day, then the later one will be used in the analysis.

Time Point (Target Study Day)	Study Day Range for UACR*	Study Day Range for Serum Chemistry, Hematology, Lipid Panel, Urinalysis, Blood and Urine Samples for Biomarkers, Vital Signs	Study Day Range for ECG, Physical Examination	Study Day Range for HbA1C
Baseline	≤ 1	≤ 1	< 1	≤ 1
Week 2 (Day 14)	2 – 21	2 - 21		
Week 6 (Day 42)	22 – 63	22 - 63		
Week 12/ET (Day 84)	64 – 104	64 – 104	≥ 1	> 1
Week 12/ET + 28 Days (Day 112)	≥ 105	≥ 105		

*: This is for the first morning void UACR sample collection.

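### SAP 7.7.2 and 6.1 conflict on unscheduled post-baseline laboratory values, and under neither rule does a laboratory table select by severity

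*SAP*

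**What the plan says.** **SAP 7.7.2** sets the post-baseline rule. For continuous tests: "For analysis by visit, the nominal study visits will be utilized". For hematology and chemistry: "shift tables presenting movement in and out of reference range from Baseline to each scheduled post-Baseline visit will be provided for each treatment group". For urinalysis: "Qualitative urinalysis laboratory results will be summarized for Baseline and all scheduled post-baseline study weeks". Baseline is treated differently, since "the Baseline value will be defined as last scheduled or unscheduled value collected prior to the first dose of treatment". In the listings: "Out-of-reference-range values will be flagged as high (H) or low (L) in the listings".

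**SAP 6.1** has a window table. One combined column covers serum chemistry, hematology, lipids, urinalysis, biomarkers and vital signs, with ranges of Days 2–21, 22–63, 64–104 and 105 onward. If a window holds several visits, scheduled or unscheduled, "the measurement closest to the target day of the visit will be used in the analysis", and a tie goes to the later value. The windows apply to by-visit analyses of the primary, secondary and other endpoints; all remaining analyses use nominal visits. SAP 3.3 names change in laboratory parameters as a safety endpoint.

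**Protocol 7.6.2.6** foresees extra tests: "Additional clinical laboratory evaluations will be performed at other times if judged to be clinically appropriate". **Protocol 7.3.3.2** lists withdrawal criteria at 3, 5 and 8 times ULN for ALT or AST. The 5-times criterion must last beyond 2 weeks. Another criterion is eGFR at or below 15, "confirmed with repeat measurement".

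**Protocol 7.10.4.4** plans shift tables against scheduled visits and counts of subjects in specified categories. It sends tests the protocol does not require to listings only. **SAP section 8** reports no changes from the planned analysis.

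**The concern.** Scheduled draws fall on Days 0, 14, 42 and 84, so the gaps are 2, 4 and 6 weeks. A criterion that needs a confirming or sustained value is likely to be completed by a draw outside that schedule. Those are the values that the laboratory tables may leave out or choose among by date.

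The issue matters for this product. Protocol section 8 names raised ALT as a non-clinical safety concern. In Study TMX-049-102 (Protocol 5.4.2) a transaminase increase at 120 mg, judged an adverse drug reaction, arose on Day 11, was mild and cleared untreated. A transient change like that can fall between visits. If a peak is sampled and then appears only in a listing, a reader comparing arms from the laboratory tables will not see it.

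**Working it through.** The plan states no figure on this point, so there is none to reproduce. The check compares the two rules and then counts days under 6.1.

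**Step 1. The two rules side by side.**

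| | SAP 7.7.2 | SAP 6.1 |
|---|---|---|
| Visit assignment | Nominal or scheduled | Study-day window |
| Unscheduled post-baseline value | Not used in by-visit or shift tables | Competes for the visit slot |
| Values kept per visit | The scheduled one | The nearest to target; a tie goes to the later |
| Selection by severity | No | No |

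Section 7.7.2 is the more specific text and probably governs. But 6.1 names these tests in its table, and laboratory change is a stated endpoint, so a programmer could follow either. The choice also moves early-termination results. A termination draw on Day 30, for example, is Visit 6/ET by nominal visit but falls in the Week 6 window (Days 22–63) under 6.1.

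**Step 2. When does 6.1 keep the repeat?** Let T be the target day, V the scheduled draw day and r the days to the repeat. For a repeat inside the window, it is kept when |V + r − T| ≤ |V − T|, that is, when V ≤ T − r/2. The permitted visit days are Days 10–18 (9 days), 35–49 (15 days) and 77–91 (15 days). The values of r are assumptions.

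| r | Week 2 (T = 14) | Week 6 (T = 42) | Week 12 (T = 84) |
|---|---|---|---|
| 3 days | V ≤ 12.5: 3/9 | V ≤ 40.5: 6/15 | V ≤ 82.5: 6/15 |
| 7 days | V ≤ 10.5: 1/9 | V ≤ 38.5: 4/15 | V ≤ 80.5: 4/15 |
| 14 days | V ≤ 7: 0/9 | V ≤ 35: 1/15 | V ≤ 77: 1/15 |

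So 6.1 admits some repeats, but each one it admits removes the scheduled value. Suppose an abnormal draw on Day 36 is followed by a normal repeat on Day 43. The distances from Day 42 are 6 and 1, so the repeat is kept and the abnormal value leaves the Week 6 table.

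**Step 3. Does another laboratory table compensate?** SAP 7.7.2 specifies no worst post-baseline value, no any-time shift and no threshold table. The categories promised in Protocol 7.10.4.4 are not defined for continuous tests. The shift tables classify values only as below, within or above range, so ALT at 1.1 times ULN and at 9 times ULN share a cell.

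**The case against.** The strongest reply is that little is hidden:

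- An untoward laboratory observation is an adverse event by definition (Protocol 7.6.2.1.1). It can reach the TEAE tables, including the table of events causing discontinuation (SAP 7.7.1).
- Withdrawn subjects have an early termination visit where possible, with chemistry and blood count in the Visit 6/ET slot.
- A repeat that confirms an abnormal scheduled value follows a value that 7.7.2 already tabulates.
- By-visit summaries give minimum and maximum, and eGFR and sUA also feed the efficacy tables.
- Everything is listed, for about 132 subjects, and safety analysis is descriptive.

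Most of this stands, and it rules out the strongest reading. A reader might infer that unscheduled results enter no table at all, or that every such draw signals a problem. The documents support neither: the routes above exist, and Protocol 7.6.2.6 also allows extra draws when ongoing data review suggests closer assessment.

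The reply does not close the gap. TEAE tables depend on investigator reporting and carry no laboratory values. An early-termination draw may come after the peak. Minimum and maximum cover only the values selected for that visit. Listings do not summarize the comparison between arms.

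It is also fair to say that Protocol 7.10.4.4 may intend extra draws to be listed only. Its wording can be read to cover off-schedule draws of a required test, or only additional analytes. If the first is meant, adding them to a table is a departure to be recorded, not a reason to leave the SAP's two rules in conflict.

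**Conclusion.** The point holds in two parts. First, SAP 7.7.2 and 6.1 give different rules for unscheduled post-baseline laboratory values, and the SAP does not rank them. Second, under either rule no laboratory table selects by severity. An abnormal unscheduled or repeat result, including one that establishes a withdrawal criterion, may appear only in a listing unless it is reported as an AE. Under 6.1 a repeat can replace the abnormal scheduled value.

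The number of results affected is unknown, because the documents give no rate of unscheduled draws. The fractions for 6.1 rest on assumed repeat intervals. They count permitted visit days, not expected subjects. The reading of 7.7.2 assumes that an unscheduled draw is not assigned a scheduled visit label in the database.

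Two further inferences should be resisted. A reader might calculate how often draws on Days 14, 42 and 84 would meet an elevation of assumed length and treat the misses as the loss. That describes the visit schedule; an elevation never sampled is lost under any table rule. A reader might also infer a bias towards one arm, but nothing in the documents shows that extra draws will differ by arm.

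The change is worth making for the safety tables. It does not affect the primary analysis.

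**What to change.** 1. In SAP 6.1, state that by-visit tables for safety laboratory tests and vital signs use nominal visits. Keep the 6.1 windows for eGFR, sUA, UACR and biomarkers as efficacy endpoints. The combined column must not simply be deleted, because eGFR and sUA come from serum chemistry and would lose their rule for multiple values.
2. In SAP 7.7.2, add a shift row from baseline to worst post-baseline value (worst low and worst high) for hematology and chemistry. Use all scheduled, unscheduled, repeat and early-termination results from the first double-blind dose to 30 days after the last dose, which is the SAP 7.7.1 TEAE window. SAP 7.7.3 has no shift tables, so this row does not extend to vital signs.
3. Add counts of subjects by worst value at the thresholds the protocol already uses: ALT or AST above 3, 5 and 8 times ULN, total bilirubin above 2 times ULN, and eGFR at or below 15. This supplies the categories promised in Protocol 7.10.4.4 and shows peak size, which the shift cells cannot. These are single-value counts and do not reproduce the duration, combined or confirmation parts of the withdrawal criteria.
4. Show the number of draws per arm. In SAP section 8, record any departure from the listing-only rule in Protocol 7.10.4.4.

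The cost is a few lines of SAP text, derived worst-value records for each test and a few extra tables, with no change to trial conduct. There are two downsides. Worst-value rates rise with the number of draws, hence item 4. The 30-day limit can also exclude some follow-up draws: Visit 7 is allowed 21 to 35 days after Visit 6/ET (28 ± 7). Those later results stay in the by-visit tables.
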